1.2 Study design

The study is an open label, single arm study with flexible dose regimen focused on assessing long-term safety and tolerability of ZS in Japanese subjects with hyperkalemia.

Correction Phase: If the subject is normokalemic (i-STAT [A portable blood analyser] potassium between 3.5 and 5.0 mmol/L, inclusive) on the morning of Correction Phase Study Day 2 after 3 doses of ZS 10 g, they will enter the Maintenance Phase. If the subject is not normokalemic, they will receive an additional 24 hours of ZS 10 g TID treatment (6 total doses). If the subject's i-STAT potassium value is between 3.5 and 5.0 mmol/L, inclusive, on the morning of Correction Phase Study Day 3, the subject will enter the Maintenance Phase. If the subject is not normokalemic, they will receive an additional 24 hours of ZS 10 g TID

treatment (9 total doses). If the subject's i-STAT potassium value is between 3.5 and 5.0 mmol/L, inclusive, on the morning of Correction Phase Study Day 4, the subject will enter the Maintenance Phase. If the i-STAT potassium value is still < 3.5 mmol/L or ≥ 5.1 mmol/L on the morning of Correction Phase Study Day 4, after 72 hours of TID treatment, the subject will be withdrawn from the study and referred to their normal health care provider for standard of care treatment. Subjects withdrawn from the Correction Phase of the study will return to the clinic 7 (± 1) days after their last dose of ZS for an End of Study (EOS) visit.

Maintenance Phase: Patients will initially be dosed with ZS at a starting dose of 5g QD. During the Maintenance Phase, the ZS dose may be increased up to 15 g QD or decreased down to 5g QOD (or 2.5 g QD) based on i-STAT potassium measurements as outlined in [Table 1](#).

Table 1 Dose Adjustment during MP

Current dose	i-STAT Potassium Value (mmol/L)	Dose Adjustment
5g QOD or 2.5 g QD	≤ 2.9	Discontinue dosing
	3.0-3.4	Discontinue dosing
	3.5-5.0	No change
	5.1-6.5	5g QD
	>6.5	Discontinue dosing
5g QD	≤ 2.9	Discontinue dosing
	3.0-3.4	5g QOD or 2.5 g QD
	3.5-5.0	No change
	5.1-6.5	10g QD
	>6.5	Discontinue dosing
10g QD	≤ 2.9	Discontinue dosing
	3.0-3.4	5g QD
	3.5-5.0	No change
	5.1-6.5	15g QD
	>6.5	Discontinue dosing
15g QD	≤ 2.9	Discontinue dosing
	3.0-3.4	10g QD
	3.5-6.5	No change
	>6.5	Discontinue dosing

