4.1.3 Visit/Time windows

In principle, analyses will be based on **nominal visit basis**, only if scheduled visit is available. In absence of scheduled visit, the unscheduled visits and discontinuation visit will be mapped according to the below windows and utilized for by-visit analysis (Table 2 and Table 3).

If scheduled visit is missing,

- If an unscheduled visit exists for that visit window, it will be used.
- If two or more unscheduled visits are available for the same window, the one closest to nominal target day will be used.

- If two unscheduled observations are equally close to target day, the last observation will be used.

As outlined in the table, S-K measurement taken within 1 day (2 days on QOD regimen) after last dose will be regarded as on-treatment and used in analysis. Unscheduled S-K measurement taken more than 1 day (2 days on QOD regimen) after last dose of ZS could be mapped to EOS (Follow up) visit.

Table 2 Visit window for correction phase

Study Visit	Nominal Day	Target Day	From	To
1	Screening (CP Baseline)		-	-1
2	CP Day 1 (CP Baseline)	1	1	1
3	CP Day 2	2	2	2
4	CP Day 3	3	3	3
5	CP Day 4	4	4	4
EOS	CP Follow Up	10	5	17

Table 3 Visit window for maintenance phase

Study Visit	Nominal Day	Target Day	From	To*
6	MP Day 1 (MP Baseline)	1	1	1
7	MP Day 2	2	2	3
8	MP Day 5	5	4	8
9	MP Day 12	12	9	15
10	MP Day 19	19	16	22
11	MP Day 26	26	23	39
12	MP Day 54	54	40	67
13	MP Day 82	82	68	95
14	MP Day 110	110	96	123
15	MP Day 138	138	124	151
16	MP Day 166	166	152	179
17	MP Day 194	194	180	207
18	MP Day 222	222	208	235
19	MP Day 250	250	236	263
20	MP Day 278	278	264	291

Study Visit	Nominal Day	Target Day	From	To*
21	MP Day 306	306	292	319
22	MP Day 334	334	320	347
23	MP Day 362	362	348	Last dose + 1 day (2 days, on QOD regimen)
EOS	MP Follow Up	last dose + 7 days	last dose +2 days (+3 days, on QOD regimen)	last dose + 14 days

*S-K measurements more than 1 day (2 days, on QOD regimen) after last dose will be regarded off-treatment and will be mapped to the EOS visit.

Note : Any available measurements regardless of scheduled or unscheduled will be taken into account when summarizing the incidence of certain event based on most extreme (lowest or highest) values in safety evaluation (e.g. analysis of incidence of hypokalemia, etc).

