The number of normokalemic days during the MP will be calculated assuming that the time interval between assessments is normokalemic only if both the beginning and end assessments for that time interval display normal S-K values. If an intermediate scheduled assessment time point is missing, then the scheduled assessment is regarded as not normokalemic. In order to determine this variable all scheduled or unscheduled fasting S-K will be taken into calculation. Descriptive statistics and 95% CI for mean for the number of normokalemic days will be provided.

- Change in S-K level from the last on-treatment Maintenance Phase visit to the End of Study

To investigate if S-K increases after stopping treatment, change in S-K from last on-treatment visit to MP EOS (MP follow up) visit will be summarized with continuous summary statistics and 95% CI for mean.

Sensitivity analysis for missing S-K values

For the mean S-K over time, longitudinal repeated measures model specified above will serve as a sensitivity check to missing S-K values. It provides estimates of S-K over time *had subjects remained on ZS for planned 52 weeks* under the Missing At Random assumption.

Further sensitivity analyses may be conducted depending on the volume of missing data as well as on the reason of study discontinuation.

Sensitivity analysis with iSTAT potassium measurements

Since the ZS dose adjustment during study is based on iSTAT measurement, analyses with categorized values (e.g. proportion of subjects with normokalemia) are expected to be sensitive to which of S-K or iSTAT K are analysed.

Summary of Potassium value over time, proportion of subjects with normokalemia and number of normokalemic days will be repeated using iSTAT potassium measurements instead of S-K values provided by Central lab. Only observed iSTAT values measured within last ZS dose + 1 day (+ 2 days on QOD regimen) will be used.

Sensitivity analysis with iSTAT potassium measurements for Correction Phase will be also carried out as outlined in section 4.2.5

Analysis with S-K adjusted for assay change bias

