4.2.7 Safety

4.2.7.1 Adverse events

Adverse events will be classified by the Medical Dictionary for Regulatory Activities (MedDRA). Adverse events will be considered Treatment-Emergent if onset is on or after first dose of ZS and on or before last dose of ZS + 1 day (+ 2days, on QOD regimen). AEs starting before 1st AEs with onset during correction phase and those with onset during maintenance phase will be separately summarized, unless otherwise specified. Adverse events starting before first dose of ZS or more than 1 day (+2days, on QOD regimen) after last dose of ZS will only be listed.

All Adverse events (including SAEs)

Summary of following TEAEs will be separately presented for Correction Phase as well as for Maintenance Phase by SOC and PT. Number and proportion of subjects with these events as well as the events rates will be provided.

- Most common AEs (i.e. reported by $\geq 2\%$ of patients based on Preferred Term)
- Any AEs
- Deaths
- Serious AEs (SAEs)
- AEs leading to drug discontinuation (DAEs)
- AEs by maximal intensity

- AEs related to study drug

In addition, incidence of AEs by MP study period (Day 1-7, Day 8-30, Day 31-90, Day 91-180, Day 181-270, Day 271-360, After Day 360) will be presented.

Adverse events of special interest (AEOSI)

Oedema-related events

Oedema related event will be defined as any of the following events (PT): Fluid overload, Fluid retention, Generalised oedema, Hypervolaemia, Localised oedema, Oedema, Oedema peripheral and Peripheral swelling.

Cardiac Failure

Cardiac Failure will be searched by SMQ “Cardiac Failure” (narrow).

Hypertension

Hypertension will be searched by SMQ “Hypertension” (narrow).

Treatment-emergent Oedema-related events, Cardiac Failure and Hypertension will be summarized by PT using as number (%) of subjects with events as well as exposure corrected event rates.

Subgroup analysis of Adverse Events

Any treatment-emergent AEs stratified by age (<65, >= 65 years, <75, >= 75 years), gender, comorbidities (HF, CKD and DM), use of medications (RAASi and Diuretics), baseline S-K (<5.5, 5.5-<6.0, >= 6.0 mmol/L), baseline eGFR (<30, 30-< 60, >= 60 mL/min/1.73m²) and baseline weight (<65, >= 65kg) will be provided by SOC and PT.

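### The Deaths and SAE tables stop at last dose + 1 day (+ 2 days on QOD), and no table of deaths and SAEs through the EOS visit is planned

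*SAP*

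**What the plan says.** SAP Section 4.2.7.1 calls an AE treatment-emergent when its onset lies between the first dose and last dose + 1 day (+ 2 days on QOD). Events that start "more than 1 day (+2days, on QOD regimen) after last dose of ZS will only be listed".

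The list of tables opens with "Summary of following TEAEs will be separately presented for Correction Phase as well as for Maintenance Phase by SOC and PT". That sentence governs any AE, deaths, SAEs, AEs leading to discontinuation, intensity and relatedness. The special-interest tables carry the same limit ("Treatment-emergent Oedema-related events, Cardiac Failure and Hypertension will be summarized by PT"), and so does the AE subgroup analysis.

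Follow-up goes further than this:

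- Section 4.1.3, Table 3, puts the Maintenance Phase EOS visit at "last dose + 7 days", with a window that closes at "last dose + 14 days".
- Section 1.2 says that subjects withdrawn in the Correction Phase "will return to the clinic 7 (± 1) days after their last dose of ZS for an End of Study (EOS) visit".

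Other safety summaries are cut differently. Section 4.2.7.3 counts vital-sign abnormalities at any post-baseline time. Section 4.2.7.2 takes the most extreme post-baseline laboratory value. Neither states a last-dose limit.

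**The concern.** Long-term safety and tolerability is the primary objective (Section 1.1). The trial has one arm and no confirmatory test (Sections 1.2 and 4.1.1), so the absolute counts are the result. A table headed Deaths that can leave out deaths occurring during the study is easily misread, and a listing gives the reader no incidence.

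The days after stopping are not arbitrary days in this trial. Section 1.2 ties stopping to significant hyperkalemia or hypokalemia, arrhythmia, congestive heart failure and end-stage renal failure, and withdraws subjects who are not normokalemic after 72 hours. Section 4.2.4.1 plans to examine potassium over the same interval ("To investigate if S-K increases after stopping treatment, change in S-K from last on-treatment visit to MP EOS"), yet no AE that starts after the cut-off in that interval is tabulated.

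The safety summaries are also uneven as written. An extreme laboratory value at the EOS visit could enter an abnormality table, while an SAE with onset that day could not enter the SAE table.

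**Working it through.** **The plan's own figure.** The SAP gives no number for this window. Its one design figure is the sample size (Section 1.3): 100 / (1 − 0.35) = 153.8, against 150 stated. In reverse, 150 × 0.65 = 97.5, against a target of 100. The figures agree approximately. The 150 is used below only as a possible denominator.

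**Inputs**

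- AE cut-off after the last dose: w = 1 day, or 2 on QOD (Section 4.2.7.1).
- Follow-up after the last dose: F = 7 days, Maintenance Phase limit 14 (Section 4.1.3); 6 to 8 days after Correction Phase withdrawal (Section 1.2).
- Maintenance Phase length for a completer: T = 362 days (Section 4.1.3).
- Dropout: 35% (Section 1.3). Its timing is not given, so two patterns are assumed.

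**Share of post-dose follow-up outside the AE tables, (F − w) / F**

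| Regimen | F = 7 | F = 14 |
|---|---|---|
| Daily dosing | 6/7 = 85.7% | 13/14 = 92.9% |
| QOD | 5/7 = 71.4% | 12/14 = 85.7% |

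**Share of all observation for a completer, (F − w) / (T + F)**

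- Daily dosing: 6/369 = 1.6%; at the 14-day limit 13/376 = 3.5%.
- QOD: 5/369 = 1.4%; at the 14-day limit 12/376 = 3.2%.

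**Share of all observation for the cohort, 35% dropout**

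- Dropout uniform over the year: mean T = 0.65 × 362 + 0.35 × 181 = 298.65 days. With F = 7 the share is 5/305.65 = 1.6% (QOD) to 6/305.65 = 2.0% (daily). With F = 14 it is 12/312.65 = 3.8% to 13/312.65 = 4.2%.
- All dropouts at Day 30: mean T = 0.65 × 362 + 0.35 × 30 = 245.8 days. With F = 7 the share is 5/252.8 = 2.0% to 6/252.8 = 2.4%. With F = 14 it is 12/259.8 = 4.6% to 13/259.8 = 5.0%.

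**Subjects withdrawn in the Correction Phase, (F − 1) / (d + F), with d dosing days**

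- d = 3, F = 6: 5/9 = 55.6% (lowest).
- d = 3, F = 8: 7/11 = 63.6%.
- d = 1, F = 8: 7/9 = 77.8% (highest).

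**Effect of one subject with an untabulated event, 1/N**

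- N = 150: 0.67 points for one subject, 1.33 for two.
- N = 100, for comparison only: 1 point for one subject, 2 for two.

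AE percentages are taken on the safety set of each phase (Sections 2.1.3 and 4.1), so the expected number of completers is not the denominator. Because Section 2.1.1 counts as enrolled everyone who signed consent, the safety sets may fall below 150, and each event would then weigh slightly more.

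**The case against.** The strongest defence is that the rule is explicit, pre-specified and coherent. It matches the on-treatment definition that the SAP uses for potassium (Sections 4.1.3 and 4.1.4) and suits the question of safety while taking the drug. Late events are still listed, so nothing is hidden. All of this stands: there is no contradiction, and the on-treatment tables need no change.

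Several stronger readings are tempting but not supported:

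- A reader might infer that the primary safety tables omit most of the follow-up collected. That is true only of the post-dose days and only of AE tables. Up to 52 weeks on treatment is fully covered, and the laboratory and vital-sign abnormality tables state no such cut-off.
- A reader might infer that a subject who becomes unwell, stops, and is recorded later is lost. The cut-off is on onset, not on recording, so that event is counted. Nor does the rule exclude a later death from an event with onset inside the window.
- A reader might infer that a late death appears in no count at all. Section 4.2.1.1 plans a follow-up disposition summary by reason for discontinuation, which might show it, although the reason categories are not given.
- A reader might take Section 4.2.4.1 to predict a potassium rise after stopping. It poses a question. The SAP gives no event rate for those days, so a higher risk there is a reasonable worry and not a documented fact.

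The length of AE collection is normally set in the protocol, which is not at hand. The 7 and 14 days used here are inferred from the EOS visit and its window.

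None of this supplies the missing table. No AE, SAE or death summary running to EOS is planned anywhere in the SAP.

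**Conclusion.** The point holds in a limited form. The Deaths and SAE tables can be incomplete for the study, because an event with onset after last dose + 1 day (+ 2 on QOD) is only listed. The untabulated time is 71% to 86% of post-dose days to the 7-day visit and about 1% to 5% of all observation. For subjects withdrawn in the Correction Phase it is about 56% to 78% of observed days, and this is where the gap matters most.

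Each affected subject changes an incidence by about 0.7 points. This assumes a safety set near 150, and how many such events will occur cannot be derived from the SAP. The shares assume that AEs are collected up to the EOS visit, and the cohort range also rests on the assumed dropout timing.

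This is an inexpensive improvement to reporting in a trial where safety counts are the main result. It does not invalidate the planned AE analysis.

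**What to change.** - Keep all on-treatment AE tables in Section 4.2.7.1 as they are.
- Add one summary of all deaths and all SAEs with onset from first dose through the EOS visit, or through the end of AE collection if the protocol sets a different limit. Show post-treatment events in a separate column, assigned to the phase of the last dose, with the safety set of that phase as denominator.
- State that the overall death count includes every death in the study, whatever the onset of the causal event.
- Extending the special-interest tables in the same way is optional.

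The cost is a few lines of SAP text and a few tables built from events that the plan already lists. The drawback is that the new table includes some off-drug events whose attribution is less clear. The separate column keeps those visible and leaves the on-treatment counts unchanged.

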4.2.7.2 Clinical Laboratory evaluation

Change from baseline over time

For continuous variables, observed values and changes from baseline to each post-baseline visit (including last on-treatment value) will be summarized by descriptive statistics.

For categorical variables, shift table from baseline to post-baseline visit (including last on treatment value) will be summarized by number (%) of subjects with each category.

Laboratory abnormalities

The incidence of hypokalemia will be evaluated by tabulating the proportion of subjects in each study phase with a lowest S-K assessment (regardless of scheduled or unscheduled) <3.5 mmol/L (mild hypokalemia) and will be repeated for a more severe definition of < 3.0 mmol/L (moderate hypokalemia) and of < 2.5 mmol/L (severe hypokalemia).

Other potentially clinically significant laboratory abnormalities will also be identified based on the most extreme (lowest and/or highest) post-baseline values and tabulated with number and proportion of subjects meeting each criterion.

Table 7 Potentially Clinically Significant Abnormalities for Laboratory Values

Variable	Unit	Low	High
Chemistry			
Calcium	mg/dL	< 7.0	> 11.0
Inorganic Phosphorus	mg/dL	< 2.0	> 6.5
Albumin	g/dL	< 2.0	> 6.0
Bicarbonate	mmol/L	< 15	> 35
Glucose	mg/dL	< 60	> 300
Potassium	mmol/L	< 3.0	> 6.0
Sodium	mmol/L	< 120	> 160
Total Protein	g/dL	< 4.0	> 10.0
Magnesium	mg/dL	< 0.9	> 4.0
ALP	IU/L	-	> 3xULN
GGT	IU/L	-	> 3xULN
AST	IU/L	-	> 3xULN
ALT	IU/L	-	> 3xULN
Total Bilirubin	mg/dL	-	> 3xULN
Hematology			
Hematocrit	%	< 28	> 55
Hemoglobin	g/dL	< 8	> 20
Platelet Count	x 10 ⁹ /L	< 50	> 600
WBC	x 10 ⁹ /L	< 2.0	> 14

Additional laboratory data summaries

Shift table for UACR categories

Shift table form subjects with UACR in categories of 0-< 30 mg/g (normoalbuminuria), 30-< 300 mg/g (microalbuminuria) and >= 300 mg/g (macroalbuminuria) will be summarized using baseline and last on-treatment values.

Shift table for eGFR categories

Shift tables for subjects with eGFR in categories of 0-< 15 mL/min/1.73 m², 15-<30 mL/min/1.73 m², 30-< 60 mL/min/1.73 m², >= 60 mL/min/1.73 m² will be summarized using baseline and last on-treatment values.

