4.2.7.3 Vital signs

Summary statistics for changes from baseline over time (including last on treatment) for each parameters (SBP, DBP and body weight) will be provided.

In addition, potentially clinically significant abnormal changes at any time post-baseline will be summarized with number of subjects and proportions.

Table 8 Potentially Clinically Significant Abnormalities for Vital Signs

Parameter	Direction	Criterion
SBP	Low	Value <= 90 mmHg and decreased >= 20 mmHg from baseline
	High	Value >= 180 mmHg and increased >= 20 mmHg from baseline
DBP	Low	Value <= 50 mmHg and decreased >= 15 mmHg from baseline
	High	Value >= 105 mmHg and increased >=15 mmHg from baseline

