4.2.7.4 ECGs

Number of subjects with clinically significant abnormality (as assessed by investigator) will be summarized for baseline and post-baseline visits. Summary for most extreme value and last on treatment evaluation will also be presented.

Summary statistics for changes from baseline over time (including last on treatment value) for each parameter (heart rate (HR), P, PR, QRS, QT and QTcF) will be provided. Here QTcF will be derived by below formula.

$$QTcF = \frac{QT}{(60 / HR)^{1/3}}$$

where, QT is in msec and HR is in bpm.

Abnormal prolongation of QTc (QTcF) will be summarized based on criteria specified in the table below. The most extreme (highest) value for a subject during treatment will be used this summary.

Table 9 **Categorical evaluation of QTc prolongation**

Parameter	Criterion
QTcF	>450 msec
	>480 msec
	>500 msec
Change from baseline in QTcF	>30 msec
	>60 msec

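### Tables 7 and 8 take extremes over all post-baseline values with no on-treatment limit, so off-drug follow-up values, notably potassium > 6.0 mmol/L, can be counted with on-treatment ones

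*SAP*

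**What the plan says.** **Open-ended rules.** After the hypokalemia incidence, SAP 4.2.7.2 states: "Other potentially clinically significant laboratory abnormalities will also be identified based on the most extreme (lowest and/or highest) post-baseline values". Potassium is a row of Table 7, with limits < 3.0 and > 6.0 mmol/L. For Table 8, SAP 4.2.7.3 says that "potentially clinically significant abnormal changes at any time post-baseline will be summarized with number of subjects and proportions". A note under Table 3 in SAP 4.1.3 adds: "Any available measurements regardless of scheduled or unscheduled will be taken into account when summarizing the incidence of certain event based on most extreme" values. None of the three gives an end of window.

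**Limited rules.** SAP 4.2.7.1 treats an adverse event as treatment-emergent only up to one day after the last dose, or two days on the every-other-day regimen; later events are only listed. SAP 4.1.3 and 4.1.4 use the same limit for on-treatment S-K and for the last on-treatment value. For QTcF, SAP 4.2.7.4 says: "The most extreme (highest) value for a subject during treatment will be used this summary".

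**Follow-up.** In Table 3 the maintenance End of Study window runs from 2 days (3 on the every-other-day regimen) to 14 days after the last dose. In Table 2 the correction-phase follow-up window runs from Day 5 to Day 17. SAP 4.2.4.1 plans a separate summary: "To investigate if S-K increases after stopping treatment, change in S-K from last on-treatment visit to MP EOS (MP follow up) visit".

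**The concern.** Laboratory values and vital signs are among the primary variables (SAP 3.1), so Tables 7 and 8 are part of the main safety result. An End of Study value is a post-baseline value, and nothing in the two table rules removes it. A subject whose potassium exceeds 6.0 mmol/L only at follow-up would then be counted in the same cell as a subject who exceeded it on drug.

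Those two events mean different things. The first describes what happens after stopping; the second describes failure of control on treatment. The SAP treats the post-stopping rise as a question of its own, yet the potassium > 6.0 row cannot separate the two. Two programmers could also produce different tables from this text and each defend the result.

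The rebound argument concerns only the potassium row. For the other rows of Table 7 and for Table 8, the point is the missing window and its inconsistency with the other safety rules.

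**Working it through.** The plan states no figure on this point, so there is none to reproduce. The check compares the data windows and then illustrates the effect of pooling.

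**1. Windows side by side**

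| Display | SAP section | End of window |
|---|---|---|
| Treatment-emergent adverse events | 4.2.7.1 | last dose + 1 day (+ 2, every other day) |
| On-treatment S-K, last on-treatment value | 4.1.3, 4.1.4 | same |
| QTcF extremes | 4.2.7.4 | during treatment |
| Table 7 laboratory extremes | 4.2.7.2 | none stated |
| Table 8 vital-sign extremes | 4.2.7.3 | none stated (any time post-baseline) |

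**2. Which off-drug potassium values exist**

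- Maintenance subjects with an End of Study value, 2 or 3 to 14 days after the last dose (Table 3).
- Subjects withdrawn after 72 hours of correction treatment because potassium was still outside the normal range, including those at or above 5.1 mmol/L. They return 7 (± 1) days after their last dose (SAP 1.2).

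**3. What other displays give for potassium**

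- On treatment: the proportion with S-K > 5.0 mmol/L at each maintenance visit and at last on-treatment (SAP 4.2.4.1). This is a different threshold and a by-visit count, not the proportion ever > 6.0.
- After stopping: the change from last on-treatment to End of Study as a continuous summary with a 95% CI (SAP 4.2.4.1). By SAP 4.1.6 this includes n, mean, SD, median, minimum and maximum. It gives no count of subjects above a threshold.
- Adverse events after the on-treatment window are listed, not tabulated (SAP 4.2.7.1).
- At the interim analysis, Appendix 8.1 leaves out the change to follow-up but keeps the other safety analyses. If End of Study values of early discontinuers are in that data cut, they could enter Table 7 with no post-stopping summary beside them.

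So no display gives the > 6.0 mmol/L incidence separately on and off drug.

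**4. Effect of pooling (assumed risks; the SAP gives none)**

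If p_on and p_off are the risks of exceeding 6.0 mmol/L on treatment and at follow-up, the pooled risk under independence is 1 − (1 − p_on)(1 − p_off). It lies between max(p_on, p_off) and p_on + p_off.

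| p_on | p_off | pooled, independent | range |
|---|---|---|---|
| 5% | 0% | 5.0% | 5–5% |
| 5% | 5% | 1 − 0.95 × 0.95 = 9.8% | 5–10% |
| 5% | 10% | 1 − 0.95 × 0.90 = 14.5% | 10–15% |
| 5% | 20% | 1 − 0.95 × 0.80 = 24.0% | 20–25% |
| 10% | 10% | 1 − 0.90 × 0.90 = 19.0% | 10–20% |

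**5. Sensitivity to the assumed potassium level**

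Take normal S-K with SD 0.5 mmol/L and 17 independent maintenance visits (Visits 7 to 23). Per-visit risk is P(S-K > 6.0), and the risk of ever exceeding is 1 − (1 − p)^17.

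- Mean 4.6: p = 0.26%, ever about 4%.
- Mean 4.8: p = 0.82%, ever about 13%.
- Mean 4.9: p = 1.39%, ever about 21%.

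One End of Study value with mean 5.1, 5.3 or 5.5 and SD 0.5 gives 3.6%, 8.1% or 15.9%.

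As a rough share of the cell, off/(on + off), an on-treatment mean of 4.6 gives 3.6/(3.6 + 4.3) = 46% to 15.9/(15.9 + 4.3) = 79%. A mean of 4.9 gives 3.6/(3.6 + 21.2) = 15% to 15.9/(15.9 + 21.2) = 43%. The share therefore depends heavily on the assumed mean.

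**The case against.** The strongest reply is that the SAP never says follow-up values are included. SAP 4.1.3 describes S-K within the on-treatment limit as what is used in analysis and sends later values to End of Study. SAP 4.1 runs safety analyses by phase. The note on extremes waives only the difference between scheduled and unscheduled values and is silent on treatment status. This stands as far as it goes: inclusion is the literal reading of an open-ended rule, not an express statement. It does not settle the matter, because the table rules and the note together admit any post-baseline measurement, while the QTcF rule shows that the authors wrote a limit where they wanted one.

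An inclusive count of rare abnormalities is also defensible in a single-arm study without confirmatory testing (SAP 4.1.1), and different displays may have different windows. That is fair, but an inclusive total can be kept alongside a split that loses nothing.

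A reader might go further and infer that neither on-treatment nor post-stopping hyperkalemia is shown anywhere, or that the post-stopping rise appears only as a mean. The SAP does not support this. Hyperkalemia > 5.0 mmol/L is tabulated by maintenance visit and at last on-treatment, and the post-stopping change is reported with median, minimum and maximum. SAP 4.2.7.2 also summarises laboratory values at each post-baseline visit, which may include End of Study. What is missing is narrower: the incidence > 6.0 mmol/L, split by treatment status.

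Nor does the SAP show that follow-up blood pressure distorts Table 8. It does not say which vital signs are taken at End of Study.

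**Conclusion.** The point holds as a specification defect in two primary safety tables. Tables 7 and 8 have no on-treatment limit, unlike the adverse-event and QTcF rules. Taken literally, they count off-drug follow-up values together with on-treatment values. The consequence is clearest for potassium > 6.0 mmol/L, where the plan itself investigates a rise after stopping and no display separates the incidence on and off drug.

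The size cannot be derived from the SAP, which gives no on-treatment mean, SD or expected End of Study level. The pooling figures rest on assumed risks, and the share figures further assume normality, SD 0.5 and independent visits; they also leave out correction-phase and unscheduled values. A reader might infer that off-drug values would make up most of the > 6.0 cell. That follows only for some inputs: the rough share runs from 15% to 79% over the means considered. The finding rests on the rule as written, not on those figures.

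**What to change.** In SAP 4.2.7.2 and 4.2.7.3, restrict the Table 7 and Table 8 extremes to the SAP's existing on-treatment window (last dose + 1 day, + 2 days on the every-other-day regimen), reported by phase. Show abnormalities from the end of that window to End of Study in a separate follow-up column. Make the note in SAP 4.1.3 say that any scheduled or unscheduled value counts within its own window.

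For potassium, report the number of subjects with S-K > 6.0 mmol/L at End of Study beside the change from last on-treatment in SAP 4.2.4.1.

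The cost is a few sentences in the SAP and one extra column per table. No new data are needed and no clinical rule changes.
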